We estimate a total sample size of 1080 children with SAM (360 per arm) and 1080 children with MAM (360 per arm) will provide at least 90% statistical power to demonstrate non-inferiority for each comparison, with a non-inferiority margin of 10 percentage points, assuming a recovery rate in the control of 77% (Table 4). For relapse outcomes, sample size will be smaller, and thus power will be lower, because only recovered children will be included in the analysis. All calculations assume a one-sided $\alpha = 0.05$ for non-inferiority and two-sided $\alpha = 0.05$ for superiority analyses.

Table 4. Sample size calculations

Scenarios with at least 80% power are **bolded**.

Primary outcome	Analysis type	Sample size per arm	Outcome prevalences reported in literature	Non-inferiority margin or detectable effect size	Assumption on control group outcome prevalence/means in sample size calculations	Power per comparison
Anthropometric recovery at discharge	Non-inferiority	360 MAM and 360 SAM children/arm enrolled; 306 MAM and 306 SAM children in analysis after 15% attrition	MAM recovery (with RUSF*): 73% (13); 73% (14); 85% (15) SAM recovery : 55.4% (16); 82.3% (17); 76% (18); 71% (pooled estimate from meta-analysis) (19)	10 percentage points (absolute difference)	55.4% (vs 45.4%)	85.6%
					77.0% (vs 67.0%)	90.0%
					82.3% (vs 72.3%)	96.8%
Relapse to wasting within 3-months post-discharge	Superiority	236 children/arm in analysis (assuming 77% of the 306 children recover)	Post-MAM relapse : 30% within 3 months (period prevalence) (20); 33% within 12-months (21) Post-SAM relapse : 6.8% 3-month cumulative incidence (22); 24% 2-month cumulative incidence (23); 30% within 3-months (unpublished); 2.6 episodes per child-year (unpublished); 1.3	35% relative reduction (incidence rate ratio = 0.65)	Incidence of 2.6 episodes per child-year	80.0%
					Prevalence of 30% (vs 20%)	71.0%

			episodes per child-year (unpublished)			
--	--	--	--	--	--	--

*RUSF = ready-to-use supplementary food

Study procedures

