### Sample size and statistical power

#### Main trial

We estimate a total sample size of 1080 children with SAM (360 per arm) and 1080 children with MAM (360 per arm) will provide sufficient statistical power to demonstrate non-inferiority for each comparison, with a non-inferiority margin of relative 12.5%, assuming a recovery rate in the control of 76% and a loss to follow up of 15% (Table 4). The sample size will be smaller for analyses of relapse, because only recovered children will be included in the analysis. All calculations assume a one-sided  $\alpha = 0.05$  for non-inferiority and two-sided  $\alpha = 0.05$  for superiority analyses,  $\beta = 0.8$ , and 15% attrition. While the key objectives of this research are to evaluate effects of the alternative RUTFs on recovery and relapse, we consider as primary outcomes any outcome for which we have adequate power for clinically or policy meaningful effect sizes (5).

 Stata commands `ssi` for continuous outcomes and `artbin` for binary outcomes were used for non-inferiority analyses, and `power twomeans` for continuous outcomes and `power twoproportions` for binary outcomes were used for superiority analyses. Outcome proportions, means, or standard deviations were taken from relevant studies in literature as delineated in Table 4.

Table 4. Calculations of detectable effect sizes for all outcomes

Outcome	Outcome prevalence in the literature	Type of analysis	Non-inferiority margin (relative) with $\geq 80\%$ power (Non-inferiority)	Detectable effect size at 80% power (Superiority)	Rank of outcome
Anthropometric recovery at discharge	MAM recovery (with RUSF*): 73% (6); 73% (7); 85% (8)  SAM recovery: 55.4% (9); 82.3% (10); 76% (11); 71% (pooled estimate from meta-analysis) (12)	Non-inferiority	12.5% relative margin		Primary
Relapse to wasting within 3-months post-discharge	Post-MAM relapse: 30% within 3 months (13); 33% within 12-months (14)  Post-SAM relapse: 6.8% 3-month cumulative incidence (15); 24% 2-month cumulative incidence (16); 30% within 3-months (unpublished)	Superiority		Risk difference of 11%; Relative risk = 0.72	Primary
Length of stay (LOS) among recovered children	MAM: 36.4 days (SD 50.4 days)(17); 5.9 weeks (95% CI: 4.9, 7.0)(18) SAM: 56 days (assumed 41 day SD) (9)	Non-inferiority	MAM: 4.9 days; 12.5% relative margin SAM: 8 days; 12.5% relative margin		Primary

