Compliance to treatment services (attendance at visits)	MAM: 87% (17) SAM: 11.1% (11)	Non-inferiority	MAM: 50% relative margin SAM: 10% relative margin		Secondary
Relapse to SAM	Note: Reporting of relapse as MAM vs SAM is not common. Daures et al reported 88.6% of relapses were MAM (23), so we apply this proportion to the below rates.  Post-MAM relapse to SAM: 30% within 3 months (13); 33% within 12-months (14)  Post-SAM relapse to SAM: 6.8% 3-month cumulative incidence (15); 24% 2-month cumulative incidence (16); 30% within 3-months (unpublished)	Superiority		MAM and SAM (Assumed to be same): RR = 0.34	Secondary
Relapse to MAM	Note: Reporting of relapse as MAM vs SAM is not common. Daures et al reported 88.6% of relapses were MAM (23), so we apply this proportion to the below rates.  Post-MAM relapse to SAM: 30% within 3 months (13); 33% within 12-months (14)  Post-SAM relapse to SAM: 6.8% 3-month cumulative incidence (15); 24% 2-month cumulative incidence (16); 30% within 3-months (unpublished)	Superiority	-	MAM and SAM (Assumed to be same): RR = 0.689	Secondary
Morbidity	MAM: 61.1% (any illness) (17) SAM: 60.0% (any illness) (9)	Non-inferiority	MAM: 17.5% relative margin SAM: 17.5% relative margin		Secondary

Anemia at discharge	MAM: 49% prevalence (21) SAM: 51% prevalence (22)	Non-inferiority	MAM: 17.5% relative margin SAM: 17.5% relative margin	--	Secondary
Anemia at 3-months post-discharge	MAM: 49% prevalence (21) SAM: 51% prevalence (22) *estimates are sourced from studies presenting data at discharge because post-discharge data not available	Superiority	--	MAM: 23.3% relative SAM: 24.2% relative	Secondary
Mortality		Non-inferiority			Exploratory

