## Statistical methods

We will conduct two separate comparisons between (i) the control group and SMS-RUTF, and (ii) between the control group and S-RUTF. All analyses will be done separately by wasting severity status (MAM vs SAM); that is, all analyses will be conducted and presented among MAM children and among SAM children separately. No adjustments for multiple comparisons will be made.

For binary outcomes, we will use log-binomial regression to estimate relative risks (RRs) and 95% confidence intervals (CIs) for the RRs, adjusting for any baseline factors as appropriate (described further below). If the regression model is adjusted, we will present both crude (unadjusted) and adjusted model results. If the models do not converge, we will use Poisson regression models with robust estimation of standard errors (26) and report which model was used. Non-inferiority will be declared if the lower bound of a one-sided 95% CI for the RR lies entirely below the non-inferiority margin of a relative 12.5%. For superiority analyses, we will use a two-sided 95% CI and superiority will be declared if the lower bound of the 95% CI for the relative risk is above 1.0. All analyses will be adjusted for health center to reflect the stratified randomization (27–29).

For continuous outcomes measured at one timepoint, we will use linear regression to estimate differences in that outcome between treatment arms, adjusting for any baseline factors as appropriate and health center (as explained above). Both unadjusted and adjusted model results will be presented.

For any outcome for which non-inferiority is demonstrated, we will then sequentially test for superiority. In these cases, we will report both non-inferiority and superiority results. The superiority analysis will be considered exploratory, as the study power calculations were based on non-inferiority effect size.

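### SAP Table 4 lists RR 0.689 as detectable with 80% power for relapse to MAM; at the listed 30% three-month rate and the recovered-only sample, power is about 57–58%

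*SAP*

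**What the plan says.** SAP Table 4 has a column headed "Detectable effect size at 80% power (Superiority"). Its entry for relapse to MAM is "MAM and SAM (Assumed to be same): RR = 0.689". The row lists published relapse rates, including "30% within 3 months (13); 33% within 12-months (14") after MAM and 6.8%, 24% and 30% after SAM. Because relapse is rarely reported by severity, the SAP cites one study in which "88.6% of relapses were MAM" and applies that share to the listed rates.

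The SAP's sample size section says the sample for relapse is smaller "because only recovered children will be included in the analysis". It assumes 360 enrolled per arm in each stratum, 76% recovery and 15% attrition. Protocol Table 4 prints the resulting sample: "236 children/arm in analysis (assuming 77% of the 306 children recover").

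The test level is agreed. The protocol sets "two-sided $\alpha = 0.05$ for superiority analyses", and the SAP's Statistical methods section says "For superiority analyses, we will use a two-sided 95% CI". That section also has MAM and SAM children analysed separately.

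**The concern.** Protocol Table 4 reports 71.0% power for relapse of 30% versus 20% at 236 per arm, which is RR 0.667. SAP Table 4 then claims 80% power for a weaker effect (RR 0.689) on a less frequent outcome (the MAM share of those relapses) in the same children. Both changes lower power, so the two entries cannot both hold at that base rate.

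What is at stake is interpretation. The SAP ranks outcomes by whether power is adequate for meaningful effects, and Table 4 is the record of that. A reader who trusts the row would take a null result as fairly good evidence against a 31% relative reduction. On the documents' inputs, the trial would miss such a reduction about 42% of the time.

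**Working it through.** **Inputs**

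- Control risk: 0.886 x 0.30 = 0.2658. The share and the rate are in SAP Table 4. Taking 30% as the control rate is an assumption, consistent with Protocol Table 4, which sets 30% against a lower 20%.
- Intervention risk at the stated effect: 0.2658 x 0.689 = 0.1831.
- Analysed n per arm per stratum: 360 x 0.85 = 306. Then 306 x 0.77 = 235.6, or 236 (protocol), and 306 x 0.76 = 232.6, or 233 (SAP).
- Two-sided 0.05, 1:1 comparison, strata separate.

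**Formula** (two proportions, pooled variance under the null)

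Power = Φ[(|p1 − p2| − 1.96 x SE0) / SE1], where SE0 = √(2p̄(1 − p̄)/n), SE1 = √((p1(1 − p1) + p2(1 − p2))/n) and p̄ is the mean of the two risks.

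**Step 1. Reproduce a printed figure.** For 30% versus 20% at n = 236, SE0 = 0.03986 and SE1 = 0.03960. So (0.1000 − 0.0781)/0.0396 = 0.552, and Φ = 71.0%. This matches Protocol Table 4, so the formula and sample are those behind that table.

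**Step 2. Apply it to the relapse-to-MAM row.** At n = 236, the difference is 0.0827, p̄ = 0.2245, SE0 = 0.03841 and SE1 = 0.03822. So (0.0827 − 0.0753)/0.0382 = 0.193, and Φ = 57.7%. At n = 233 the result is 57.1%. Unpooled, log-RR and arcsine versions at n = 236 give 58.0%, 56.7% and 57.9%.

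**Step 3. Solve for the effect with 80% power.** At n = 236, p2 = 0.160 and RR = 0.604. At n = 233, RR = 0.601. To have 80% power at RR 0.689 would take about 399 analysed children per arm, more than the 360 enrolled.

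**Step 4. Try every listed base rate** (n = 236, each multiplied by 0.886):

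| Listed rate | Control risk | Power at RR 0.689 | RR at 80% power |
|---|---|---|---|
| 33% (12 months) | 29.2% | 63.0% | 0.625 |
| 30% (3 months) | 26.6% | 57.7% | 0.604 |
| 24% (2 months) | 21.3% | 46.5% | 0.551 |
| 6.8% (3 months) | 6.0% | 15.0% | 0.202 |

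Using n = 233 lowers each power by at most about 0.6 points. Leaving the 30% unscaled gives 64.5% (detectable RR 0.631).

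**Step 5. Relax the sample.** With a 26.6% control risk, all 306 retained children give 68.9% and all 360 enrolled give 75.9%. Pooling MAM and SAM at about 472 per arm gives about 86%, but the SAP rules pooling out.

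**Step 6. Where 0.689 might come from.** If 26.6% is treated as the lower risk and the higher risk is sought at 80% power, the answer is 38.7% (n = 233) or 38.6% (n = 236). The inverted ratios are 0.686 and 0.688. In the relapse-to-SAM row the base is 0.30 x 0.114 = 0.0342, and the same reversal gives 0.347 to 0.348 against the stated 0.34. In the stated direction, RR 0.34 from 3.42% has about 37% power.

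**The case against.** The row prints neither its control rate nor its analysed n, so 26.6% and 233 to 236 are inferred. RR 0.689 would reach 80% power at a control risk near 39%. That stands as a limit on the replacement figure: 0.60 is tied to the 30% base. It does not rescue the row, because the documents give no such rate for relapse to MAM and all the listed rates fall short.

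The outcome is also secondary, no decision rule uses 0.689, and the trial was sized on recovery. The protocol says openly that relapse power is lower. All of this is correct and limits the consequence to one planning figure.

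A reader might infer that the authors used all 360 enrolled children and the 12-month 33% rate, ignoring their own recovered-only restriction and three-month window. That combination does pass 80% (80.9% power at RR 0.689), but its detectable RR is 0.692, not 0.689. The reversed-direction route comes closer with the recovered-only sample and the three-month rate. The documents state neither route, so the charge that the restriction was ignored is not supported.

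The reversal is not established either. It matches 0.689 and 0.34 closely but not exactly, and for overall relapse at 30% it gives 0.707 to 0.708 against the stated 0.72.

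**Conclusion.** The row is wrong as written on the documents' own inputs. With a 26.6% control risk and 233 to 236 recovered children per arm in a stratum, RR 0.689 has about 57–58% power rather than 80%. The effect detectable with 80% power is RR about 0.60, a reduction of roughly 40% rather than 31%. With the 24% base the figures are about 46–47% and 0.55.

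The size rests on three assumptions: the listed 30% three-month rate is the control rate, the 88.6% share applies to it, and recovery and attrition are as planned. That 80% is not reached at the recovered-only sample does not depend on which listed rate is chosen. How 0.689 was obtained remains unknown.

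It would be wrong to infer that the trial is undersized for its main non-inferiority question. The sample of 360 per arm per stratum was justified on recovery and is unaffected.

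**What to change.** In SAP Table 4, restate the relapse-to-MAM entry in one of two ways: RR about 0.60 at 80% power (236 per arm, 26.6% control risk), or about 58% power for RR 0.689. State in the row the control rate, the analysed n per arm and which arm carries the higher risk. If another base rate was intended, name it and give the matching figure, for example RR about 0.55 for the 24% rate.

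Recheck the relapse-to-SAM and overall relapse rows in the same way, so that the table is consistent and any reversal of direction is caught.

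The cost is SAP wording and a short recalculation. Design, data collection and analysis do not change, but the stated detectable effect becomes less favourable.

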### Sub-study 1: Acceptability

A total sample size of 102 children was targeted based on recommendations in UNICEF protocols for acceptability testing of novel RUTF products, the requirement for complete sequences in a 3×3 full Latin square crossover design, and statistical power considerations. The sample size is consistent with the statistical power considerations, assuming a non-inferiority margin of 4 grams per observed intake in 30 minutes from a test dose, a between-subject standard deviation (SD) of 6.75 grams per kilogram body weight from literature, a conservative intra-class correlation (ICC) of 0.3, and an overall alpha (two-sided) of 0.05 (translating to a one-sided alpha of 0.025 for a non-inferiority test), 90% power, and attrition rate of 20%.

### Sub-study 2: Microbiome and gut health

We calculated the required number of participants based on expected species richness indices from a rural Gambian cohort study that compared interactions between the fecal gut microbiome, enteric pathogens, and energy-regulating hormones among acutely malnourished children (24). We anticipate a species richness index of 49 (SD ± 23) in relapse cases (equivalent to Gambian children with SAM) and 64 (SD ± 27) in non-relapse cases (equivalent well-nourished Gambian children). Using a significance level of 0.05 and a desired power of 80%, we estimated a sample size of 44 participants per group. The effect size, a difference of 15 in species richness, is clinically meaningful and is justified by the study conducted in Gambia. We expect relapse to occur in 10% of children in Burkina Faso, and thus a total sample of 489 recruited children will likely yield 44 cases of relapse, accounting for 10% loss to follow up.

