¹ Enteropathogen detection will be conducted using the TaqMan Array Card (TAC) system, a 384-well singleplex real-time PCR format used to detect 62 infection targets including viruses, bacteria, protozoa and helminths, specifically: *A. duodenale* & *lumbicoides*; *B. fragilis* & *hominis*; *C. belli*, *cayetanensis*, *coli*, *concisus*, *difficile*, *hominis*, *jejuni*, *parvum*, *troglydytis*, & *upsaliensis*; *E. bieneusi* & *histolytica*; *G. lamblia*; *H. pylori*; *M. tuberculosis*; *N. americanus*; *P. shigelloides*; *S. enterica*, *flexneri*, *masoni*, *sonnei*, & *stercoralis*; *T. solium* & *trichiura*; *V. cholerae*; enteroaggregative *E. coli* [EAEC (aaiC, aatA, & aagR)], enteroinvasive *E. coli* [EIEC (*Shingella* spp.)], enteropathogenic *E. coli* [EPEC (bfp1 & eae)], enterotoxigenic *E. coli* [ETEC (LT, STx, & STp)], and Shiga toxin (stx1 & stx2) producing *E. coli*; *Campylobacter* pan. & *Entamoeba* pan.; *Aeromonas* spp., *Cryptosporidium* spp., *Encephalitozoon* spp., & *Schistosoma* spp.; adenovirus (serotypes 40 and 41), astrovirus, Epstein-Barr virus (EBV), norovirus (GI/GII & GI.1/GII.4), rotavirus, and sapovirus; antibiotic resistance genes, including: β -lactam (CTX-M, TEM, SHV), carbapenemases/carbapenems (KPC, NDM, MCR-1, OXA), macrolide (ermB, mphA), and quinolone (QnrA, QnrB1, QnrB4, QnrS).

be characterized using shotgun metagenomics to analyze bacterial DNA. Metagenomic data will be processed into abundance tables using R (R core team, 2021). Alpha and beta diversity parameters will then be computed and compared between treatment arms. A differential abundance analysis will be performed to identify bacterial taxa whose abundance is significantly altered by the milk- and peanut-free RUTF relative to the standard RUTF.

Fecal samples will be collected for storage for these later analyses of the interventions' effects on gut health biomarkers at a sub-set of 5 of the study health centers (approximately 60 children per study arm, to total 180 children with SAM).

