#### Sub-study 2: Microbiome and gut health

This nested sub-study will recruit children with SAM at a sub-set of 5 of the 30 study facilities in the main trial. Inclusion criteria for this sub-study therefore include age 6-59 months, MUAC < 115 mm or WLZ/WHZ < -3, absence of clinical complications, passing the appetite test, accompanied by caregiver or legal guardian, and caregiver consent. Exclusion criteria include needing hospitalization, known RUTF ingredient allergies, already enrolled in a MAM or SAM treatment program, physical abnormalities that cause measurement issues, or plans to move away within six months.

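### The microbiome sub-study's 489 recruits and 44 relapses omit the recovery step, and the 489 is not reconciled with the Protocol's 180 children

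*SAP*

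**What the plan says.** The SAP's sample-size paragraph for Sub-study 2 (Microbiome and gut health) compares species richness between children who relapse and children who do not. It expects a "species richness index of 49 (SD ± 23) in relapse cases" and "64 (SD ± 27) in non-relapse cases", and treats "a difference of 15 in species richness" as clinically meaningful. "Using a significance level of 0.05 and a desired power of 80" per cent, "we estimated a sample size of 44 participants per group". It then assumes that 10% of children relapse and concludes that "a total sample of 489 recruited children will likely yield 44 cases of relapse, accounting for 10% loss to follow up".

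On sites, the SAP's eligibility section states: "This nested sub-study will recruit children with SAM at a sub-set of 5 of the 30 study facilities in the main trial". The Protocol's fecal sample sub-study also uses 5 health centers, but plans "approximately 60 children per study arm, to total 180 children with SAM". The Protocol attaches no power statement to that number.

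SAP Table 1 and Protocol Table 3 both define relapse as a new episode among children who recovered from the index episode. The footnote to the SAP's accrual figure adds the requirement of at least one post-discharge visit.

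**The concern.** There are two separate problems.

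The first is a missing step. A child who never recovers cannot relapse under the plan's definition. Both documents allow for this in the main trial: Protocol Table 4 reduces 306 children to 236 by applying 77% recovery, and the SAP's main-trial sample-size section says that the relapse sample will be smaller for the same reason. The microbiome paragraph makes no such reduction.

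The second is a conflict of size. The two documents give 180 and 489 children for a sub-study at the same number of facilities, and neither explains the difference.

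At stake is whether the 80% power claim for the sub-study's named primary outcome describes the sample that will be collected. If it does not, a null result could be read against power that the sample never had.

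**Working it through.** **Inputs.** From the SAP's Sub-study 2 paragraph: SDs 23 and 27, difference 15, α = 0.05 (taken as two-sided, since only that gives 44; one-sided gives 35), relapse 10%, loss 10%. Recovery: 76% (SAP main-trial sample size) or 77% (Protocol Table 4). Total SAM enrolment 1080, facilities 30 (both documents). Post-SAM relapse rates in SAP Table 4: 6.8%, 24% (2-month) and 30%.

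**Step 1: reproduce the plan.**
- n per group = (1.960 + 0.842)² × (23² + 27²)/15² = 7.849 × 1258/225 = 43.9, so 44.
- Recruits = 44/0.10/0.90 = 488.9, so 489.

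Both figures reproduce exactly, with no recovery factor.

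**Step 2: add recovery.** Expected relapses = N × recovery × follow-up × relapse.
- 489 × 0.76 × 0.90 × 0.10 = 33.4; at 77%, 33.9.
- Recruits for 44 relapses: 44/(0.10 × 0.90 × 0.77) = 634.9; at 76%, 643.3.

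**Step 3: power at 489.** Power is from the noncentral t with Welch degrees of freedom and noncentrality 15/√(23²/n₁ + 27²/n₂), where n₁ is relapsers and n₂ non-relapsers. A 10% relapse rate gives a split of about 1:9.

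| Comparison at 489 | n₁ vs n₂ | Power |
|---|---|---|
| No recovery step, all non-relapsers | 44 vs 396 | 98% |
| 76% recovery, all non-relapsers | 33.4 vs 301 | 93% |
| 76% recovery, controls matched 1:1 | 33.4 vs 33.4 | 67% |
| 77% recovery, controls matched 1:1 | 33.9 vs 33.9 | 68% |

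**Step 4: relapses needed for 80% at a 1:9 split.** 22 vs 198 gives 78.5%; 23 vs 207 gives 80.4%. So about 23 relapses are needed. Recruits: 23/(0.10 × 0.90 × 0.77) = 331.9 and 23/(0.10 × 0.90 × 0.76) = 336.3, that is about 332–336.

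**Step 5: the two sizes.** Assuming an even caseload, 1080/30 = 36 children with SAM per facility, and 5 × 36 = 180, the Protocol's figure. The SAP's 489 is 489/180 = 2.7 times that: about 98 per facility, or 489/1080 = 45% of all SAM enrolment.

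**Step 6: power at 180, all non-relapsers compared.**
- 10% relapse, no recovery step: 180 × 0.90 × 0.10 = 16.2 vs 145.8, power 64%.
- 10% relapse, 76% recovery: 180 × 0.76 × 0.90 × 0.10 = 12.3 vs 110.8, power 51%.

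Over the listed rates, with 180 × 0.76 × 0.90 = 123.1 children at risk:

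| Relapse rate | Relapses vs non-relapses | Power |
|---|---|---|
| 6.8% | 8.4 vs 114.7 | 36% |
| 10% | 12.3 vs 110.8 | 51% |
| 24% | 29.5 vs 93.6 | 83% |
| 30% | 36.9 vs 86.2 | 87% |

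A normal approximation is too generous with so few relapses: it gives 69% and 57% where the t-based figures are 64% and 51%.

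**The case against.** The strongest reply is that 489 may be a deliberate revision. The Protocol's 180 serves a comparison of gut markers between arms. The SAP adds an objective relating gut health to relapse and sizes the sub-study for that. The SAP is also the later document: its sensitivity-analysis text describes product switching near the end of the study in the past tense. This stands as a possibility. It is why 180 cannot be taken as the planned size, and why a reader who infers that the sub-study is underpowered goes further than the documents allow. It does not remove the conflict: the SAP keeps 5 facilities, does not mention 180, and says that the sub-studies were included in the main protocol.

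A reader might also infer that 489 cannot be reached at 5 facilities. The documents do not show that. They give no caseloads and do not say how the 5 sites are chosen, so 36 per facility is only an average.

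Nor does the missing recovery step by itself bring power below target. At 489, with all non-relapsers compared, power is about 93%, because the equal-group formula overstates the relapses needed at a 1:9 split. That comfort depends on an unstated choice: the paragraph speaks of 44 per group and does not say whether controls would be matched.

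The 10% could be read as 10% of all recruited children, which would answer the recovery point. The SAP does not say so, and its relapse definition points the other way.

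Finally, the SAP calls this sub-study exploratory, and no main-trial conclusion rests on it. That limits the consequences, but the paragraph still makes a formal power claim for a named primary outcome.

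**Conclusion.** Wrong as written. On the plan's own relapse definition and 76–77% recovery, 489 recruits yield about 33–34 relapses, not 44. This needs no assumption beyond reading the 10% as a rate among recovered children. Its effect on power depends on the comparison group: about 93% with all non-relapsers, about 67–68% with 1:1 matching.

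The 180 and 489 are unreconciled. If 180 is the number sampled, power at the SAP's 10% relapse rate is 51–64%, where the lower figure includes 76% recovery. This shortfall is conditional on both 180 and 10%: with 76% recovery, power at 180 passes 80% at the listed 24% and 30% rates and falls to about 36% at 6.8%. The SAP does not explain why it chose 10% from within that range, so neither adequate nor inadequate power at 180 can be asserted from the documents.

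**What to change.** Change the text as follows:

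1. State one sub-study N and one facility count, the same in both documents. If 489 replaces 180, say so and why.
2. Restate expected relapses as N × recovery × follow-up × relapse, with each factor given.
3. Say whether relapsers are compared with all non-relapsers or with matched controls, and compute power for that split with a t-based method. With all non-relapsers and 10% relapse, about 23 relapses, or about 332–336 recruits, give 80%.
4. Justify the 10% relapse rate against the 6.8–30% in SAP Table 4, and show power over that range.

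The change needs no extra children. The cost is that the stated yield falls, and the stated power falls too if 180 is the real size and 10% is kept.
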